5.2 Secondary endpoints

The study's secondary endpoints are the Low- and high-tech anterior segment parameters (NIBUT, TBUT, Oxford class).

For these parameters, the changes occurring in the two groups at each visit compared to baseline will also be evaluated.

5.3 Safety endpoints

Safety assessments will consist of recording all adverse events, adverse device effects, and product deficiencies.

6. PATIENT SELECTION CRITERIA

6.1 Study participants

65 patients will be enrolled.

6.2 Inclusion criteria

- 18 years or older
- provided written informed consent
- OSDI score of 13 or more at the baseline visit after at least two months of first-line therapy (artificial tears and warm compresses)
- Clinical diagnosis of MGD
- Type 1 Schirmer test > 10 mm
- No previous history of allergy or sensitivity to doxycycline,
- No use of additional topical or systemic antibiotics for the prior 2 months
- No use of topical anti-inflammatory agents (ex: corticosteroids or cyclosporine) for the prior 3 months.

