4. STUDY DESIGN

4.1 Study Description

This spontaneous, prospective, non-randomized, parallel-group, phase IV study was conducted in compliance with the tenets of the Declaration of Helsinki.

All study participants were fully consented, and written informed consent was obtained.

This study included patients with refractory MGD. Refractory MGD is defined as symptomatic MGD (OSDI > 13 points) despite 2 months of first-line treatment with lacrimal substitutes 3 times per day and meibomian gland expression with warm compresses twice per day.

The study will consist of 3 visits: Visit 1(Baseline - day 0), Visit 2 (day 90 ± 5 - 3rd month), Visit 3 (day 180 ± 5 - 6 month). At each visit, patients will receive an OSDI questionnaire, NIBUT, type I Schirmer test and AS assessment, including TBUT, corneal staining (Oxford scale)

At baseline, eligible patients will be enrolled and treated with the assigned protocol. The investigators will assign the protocol (non-randomized) in a 1:1 ratio.

At Visit 2, NIBUT, TBUT, Oxford scale and OSDI improvement will be evaluated compared with Visit 1. Patients will be carefully asked about their compliance with the treatment. Patients who interrupted the treatment for adverse events or low compliance (<75% of the protocol adherence) will exit the study and be excluded from the analysis.

At Visit 3, the study population will be evaluated as done in Visit 2

The protocols in the study are the following:

- LCD (low-dose continuous protocol) - 50 mg of doxycycline for three months
- FPP (Full-dose pulsed protocol) - 100 mg of doxycycline for the first 15 days of the month for three months.

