5. STUDY ENDPOINTS

5.1 Primary endpoints

The primary endpoint of this study are:

- OSDI
- Number of patients with OSDI improvement > 7 points (clinically significant)

Clinical Trial Protocol CPDOXY1

Comparison between continuous and pulsed oral doxycycline treatment protocols for refractory meibomian gland dysfunction - 9 months follow-up prospective study

For these parameters, the changes occurring in the two groups at each visit vs baseline will be evaluated.

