11.3.1.1 Primary efficacy endpoint

Paired t-test will be used to study OSDI. Chi-square is used to study clinically significant OSDI variation

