14.7 Study timetable and end of study

	Visit 1 (day 0)	Visit 2 (day 90)	Visit 3 (day 180)
Verify inclusion and exclusion criteria	X		
Informed consent signature	X		
OSDI questionnaire	X	X	X
NIBUT	X	X	X
AS assessment of blepharitis and hyperemia	X	X	X
TBUT	X	X	X
Adherence to study treatments		X	
Prescribe study drug	X		

Clinical Trial Protocol CPDOXY1

Comparison between continuous and pulsed oral doxycycline treatment protocols for refractory meibomian gland dysfunction - 9 months follow-up prospective study

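### The Visit 1 OSDI both admits the patient and serves as the 'before' value of the primary within-arm analysis, so part of any within-arm fall can be regression to the mean; the LCD versus FPP contrast is not biased by this when the arms have similar baseline OSDI

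*Protocol*

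**What the plan says.** Entry depends on the OSDI read at the first study visit. Protocol 6.2 asks for an "OSDI score of 13 or more at the baseline visit after at least two months of first-line therapy". Section 4.1 makes Visit 1 the baseline ("The study will consist of 3 visits: Visit 1(Baseline - day 0"), and the timetable in 14.7 places both "Verify inclusion and exclusion criteria" and the first OSDI at Visit 1. No earlier qualifying OSDI is described.

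The primary endpoints in 5.1 are OSDI and the "Number of patients with OSDI improvement > 7 points (clinically significant"). For both, "the changes occurring in the two groups at each visit vs baseline will be evaluated". Section 11.3.1.1 names the tests: "Paired t-test will be used to study OSDI", and "Chi-square is used to study clinically significant OSDI variation". Section 4.1 describes two doxycycline arms, assigned 1:1 by the investigators without randomization, and no untreated arm.

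The threshold is worded in two ways. Section 6.2 includes a score of exactly 13, while 4.1 does not: "Refractory MGD is defined as symptomatic MGD (OSDI > 13 points) despite 2 months of first-line treatment".

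**The concern.** OSDI varies from one reading to the next. A patient near the threshold who happens to score high at Visit 1 is admitted, and one who happens to score low is not. The admitted group's Visit 1 mean is therefore somewhat too high, and the next reading is expected to be lower whether or not the treatment does anything.

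The two months of first-line therapy before entry do not prevent this, because the score that decides entry is still the Visit 1 score. The worst-eye rule in 11.3.1 is irrelevant here, because OSDI is one score per patient.

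A test that compares each patient with their own Visit 1 score counts this fall as improvement. At stake is the meaning of a significant within-arm OSDI change, and of each arm's percentage of clinically significant improvers.

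**Working it through.** **The plan's own figure.** Section 11.2 is the only calculation in the protocol. It sizes a before-after paired t-test on break-up time with a change of 1 s, SD 2.3 s, one-tailed 2.5% and 80% power. (2.3 × (1.960 + 0.842) / 1)² = 41.5, so 42; adding the small-sample term 1.960²/2 gives 43.4. Exact power is 79.5% at 43 and 80.5% at 44. The stated 43 is reproduced to within a patient or so. It says nothing about OSDI, but it shows that the protocol itself thinks in before-after terms.

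**Inputs for OSDI.** From the protocol: entry at 13 or more, responder cut above 7 points, 65 patients at 1:1, so about 32 per arm. Assumed, because the protocol gives none of these: normal scores in the source population with mean/SD of 20/12, 25/15 or 35/18; retest reliability r of 0.6 to 0.9; no true change.

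**Formulas.** With c = (13 − mean)/SD and λ = φ(c)/(1 − Φ(c)):
- expected fall = (1 − r) × SD × λ
- variance of the change = (1 − r)² × SD² × (1 + cλ − λ²) + (1 − r²) × SD²
- rejection rate of the paired test from the noncentral t, with noncentrality = fall / SD of change × √n
- share improving by more than 7 with no entry threshold = 1 − Φ(7 / (SD × √(2(1 − r)))). The share after selection was simulated.

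**Central case (25/15, r = 0.7).** c = −0.80 and λ = 0.2897/0.7881 = 0.368. Fall = 0.3 × 15 × 0.368 = 1.65 points. Variance of the change = 0.09 × 128.4 + 0.51 × 225 = 126.3, so SD 11.24. Noncentrality at n = 32 is 1.65/11.24 × 5.66 = 0.83, which gives 12.7% rejection at a two-sided 5% level. Improvers by more than 7 points: 27% with no threshold, 32% after selection. Worseners by more than 7 after selection: 22%.

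**Range (first value r = 0.6, second r = 0.9).**

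| Mean/SD | Fall, points | Rejection, n = 32 | Improve >7, no threshold | Improve >7, selected |
|---|---|---|---|---|
| 20/12 | 2.24; 0.56 | 22.6%; 8.9% | 25.7%; 9.6% | 31.9%; 11.3% |
| 25/15 | 2.21; 0.55 | 15.6%; 7.4% | 30.1%; 14.8% | 35.2%; 16.6% |
| 35/18 | 1.53; 0.38 | 8.4%; 5.8% | 33.2%; 19.2% | 36.1%; 20.4% |
| 40/12 | 0.15; 0.04 | 5.1%; 5.0% | 25.7%; 9.6% | 26%; 9.7% |
| 40/18 | 1.00; 0.25 | 6.4%; 5.3% | 33.2%; 19.2% | 35.0%; 19.9% |

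The range of 0.4 to 2.2 points belongs to the first three rows, not to every pairing of those means and SDs. At 20/18 and r = 0.6, for example, the fall is 4.1 points.

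**Between arms.** A simulation at 20/12, r = 0.7, with 32 comparable patients per arm and no effect gave 5.2% rejection for a between-arm t-test on change and 5.3% for the chi-square, both at nominal 5%. In the same simulation, the within-arm paired test declared improvement in 18% of arms against a nominal one-sided 2.5%. If the arms differ in baseline OSDI by D points, the expected changes differ by (1 − r) × D. With D = 5 (assumed) and r = 0.7, that is 1.5 points with no difference between regimens.

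**The case against.** The strongest reply is that the objective in 3.1 asks which of two protocols has the greater impact. A shift common to both arms cancels in that comparison, and the chi-square on responders is naturally read as between arms. This stands when baseline OSDI is similar. A reader might infer that the double use of the Visit 1 score invalidates the comparison of regimens. The documents do not support that, and the simulation contradicts it for comparable arms. What remains is that the test written for continuous OSDI is within-patient, where nothing cancels, and that investigator-chosen assignment does not assure similar baselines.

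Second, the size rests wholly on assumptions. This also stands. If most candidates score well above 13, the effect nearly vanishes.

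Third, a reader might credit selection with the whole share of unchanged patients counted as responders, roughly 11 to 36% in the first three scenarios. That is wrong: about 10 to 33% would exceed 7 points with no entry threshold at all, through ordinary retest variation.

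Fourth, the harm arises only because a paired test is named for a between-protocol question, so it may look like a side-effect of that mismatch. That is largely fair, and the fix below addresses both. The point still matters separately because within-arm changes and responder percentages will probably be tabulated whichever test is primary.

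**Conclusion.** The point holds for within-arm results. The admitting score is also the 'before' score and there is no untreated arm, so with any reliability below 1 the paired t-test on OSDI exceeds its nominal level when nothing has changed. Under the three assumed populations, the spurious fall is about 0.4 to 2.2 points and rejection is about 6 to 23% in an arm of 32. Selection adds about 1 to 6 percentage points to the responder share. At a source mean of 40, rejection is about 5 to 6%.

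Even the largest of these mean falls is under a third of the protocol's own 7-point criterion (2.24/7 = 0.32), so this artefact alone would not explain a large observed fall. A reader might also infer that the sponsor intends to claim each regimen works against no treatment. The protocol states no such objective. The risk is that a significant paired test, as the named primary analysis, would be read that way.

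**What to change.** In 11.3.1.1:
- State that within-arm OSDI change (paired t-test) and each arm's responder percentage are descriptive and are not evidence that a regimen works.
- Rest the primary conclusion on the LCD versus FPP comparison of OSDI change, adjusted for baseline OSDI.
- Report the percentage worsening by more than 7 points beside the percentage improving by more than 7. Retest variation alone feeds both sides about equally, so the pair shows the reader how much of the improver count is noise.

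Reconcile the threshold wording in 4.1 and 6.2, which differ for a score of exactly 13. Otherwise leave the entry rule as it is. Qualifying patients on an earlier questionnaire would remove the artefact, but it would need contact and consent before Visit 1. It would also admit patients below the symptom threshold in 4.1, including some with scores too low to improve by more than 7 points.

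The cost is a paragraph and a table row. The downside is that within-arm results can no longer be presented as confirmatory, and the conclusion rests on a between-arm comparison for which 11.2 gives no sample-size basis. Baseline adjustment deals with unequal OSDI at entry, not with other differences that investigator assignment may create.

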6.3 Exclusion criteria

- Active ocular inflammation in either eye,
- Demodex blepharitis,
- Ocular surgery within the past 3 months of baseline examination,

Clinical Trial Protocol CPDOXY1

Comparison between continuous and pulsed oral doxycycline treatment protocols for refractory meibomian gland dysfunction - 9 months follow-up prospective study

- Structural ocular surface and eyelid abnormalities.
- Sjögren's syndrome
- Rheumatoid arthritis
- Other systemic diseases resulting in dry eye
- Known autoimmune disease
- Doxycycline allergy or sensitivity
- History of antibiotic therapy at any time within 2 months of the commencement of study
- Use of significant calcium supplementation or other medications that could interfere with doxycycline absorption (es: Iron supplementation)

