1.3 Devices under study

The drug in the study is oral doxycycline, which is the most commonly used oral tetracycline for treating posterior blepharitis and MGD. The rationale for using tetracyclines is based in part on small clinical trials that have reported the drugs' effectiveness in improving symptoms in patients with ocular rosacea and in improving tear break-up time in patients with rosacea and MGD. [1]

Doxycycline is a metal ion chelator and a broad-spectrum antibiotic that prevents access of acyl t-RNA to the acceptor site on the mRNA-30s ribosomal subunit complex. In addition to these established functions, other properties that have recently been ascribed to

Clinical Trial Protocol CPDOXY1

Comparison between continuous and pulsed oral doxycycline treatment protocols for refractory meibomian gland dysfunction - 9 months follow-up prospective study

doxycycline include differential inhibition of the activity of members of the matrix metalloproteinase (MMP) family, inhibition of MMP synthesis, inhibition of interleukin-1 synthesis, inhibition of activated B cell function, inhibition of nitric oxide (NO) synthesis by lipopolysaccharide activated macrophages, and inhibition of collagen synthesis by cultured chondrocytes. [3]

Tetracyclines also decrease lipase production in both *S. epidermidis* and *S. aureus*. However, it's worth noting that tetracyclines can cause photosensitization, gastrointestinal upset, vaginitis, and, rarely, azotemia. Tetracyclines have been implicated in cases of pseudotumor cerebri, and their metabolism may alter the effectiveness of certain medications (e.g., decrease the effectiveness of oral contraceptives and potentiate the effect of warfarin). Tetracyclines are contraindicated in pregnancy, for nursing women, and for patients with a history of hypersensitivity to tetracyclines. Furthermore, tetracyclines should not be used in children under 8 years of age since staining of teeth may occur; however, oral erythromycin may be used as an alternative. [1-2-3]

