7. STUDY TREATMENT

7.1 Study supplies

Study treatment will be prescribed to the patient as for normal clinical practice

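### The allergy criteria screen for doxycycline only, although the protocol contraindicates the drug after hypersensitivity to any tetracycline

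*Protocol*

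**What the plan says.** Section 1.3 introduces oral doxycycline as the study drug, "which is the most commonly used oral tetracycline for treating posterior blepharitis and MGD". It then gives the contraindications for the class as a whole: "Tetracyclines are contraindicated in pregnancy, for nursing women, and for patients with a history of hypersensitivity to tetracyclines".

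The eligibility lists handle allergy twice, both times for the single drug. Section 6.2 asks for "No previous history of allergy or sensitivity to doxycycline". Section 6.3 excludes "Doxycycline allergy or sensitivity".

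The other item that could catch a patient with a class reaction is the antibiotic washout. Section 6.3 words it as "History of antibiotic therapy at any time within 2 months of the commencement of study", and section 6.2 has a matching 2-month item.

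On timing, section 4.1 states: "At baseline, eligible patients will be enrolled and treated with the assigned protocol". The timetable in section 14.7 places verification of the criteria and prescription of the drug at the same Visit 1. Section 7.1 adds: "Study treatment will be prescribed to the patient as for normal clinical practice".

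**The concern.** The contraindication covers a class and the screen covers one member of it. Someone who reacted to a different tetracycline, and has never knowingly reacted to doxycycline, falls under the first and not the second. An investigator who applies sections 6.2 and 6.3 exactly as written would enrol that person, and no protocol deviation would be recorded, because no criterion was broken.

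What is at stake is the safety of that patient. Both arms receive doxycycline, so no bias between arms is claimed, and neither the sample size nor the efficacy analysis depends on the point. Eligibility criteria belong in the protocol, so this is not something that would ordinarily be left to a separate analysis plan.

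**Working it through.** The main check is a comparison of text; the protocol states no figure to reproduce.

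**Step 1: who is covered by which rule**

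| Patient's history | Contraindicated under 1.3 | Stopped by 6.2 or 6.3 |
|---|---|---|
| Known reaction to doxycycline | Yes | Yes, by the allergy item in both lists |
| Reaction to another tetracycline taken within the last 2 months | Yes | Yes, by the antibiotic washout |
| Reaction to another tetracycline more than 2 months ago, no known doxycycline reaction | Yes | No |

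Only the third row is open. An example is an adult who reacted to minocycline years ago, has never taken doxycycline, has had no antibiotic in the past 2 months and is otherwise eligible. That patient satisfies each item of 6.2 and triggers none of 6.3.

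**Step 2: is there a check elsewhere?** Sections 7.1 to 7.5, 10.1 and the timetable in 14.7 contain no question about allergy to the class. Eligibility is verified and the drug prescribed at one visit, so the written criteria are the only screening step that the protocol defines before the first dose. After that, under section 7.3, patients take the drug at home unsupervised.

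**Step 3: is earlier exposure more likely in this population?** Section 1.2 names minocycline and tetracycline as options for this disease, so such exposure is possible. The definition of refractory disease does not make it more likely: section 4.1 requires symptoms "despite 2 months of first-line treatment with lacrimal substitutes 3 times per day", together with warm compresses, and does not require a failed antibiotic.

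**Step 4: size, on an assumed prevalence**

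Inputs:
- n = 65 enrolled (section 6.1).
- p = share of otherwise eligible patients with an older reaction to another tetracycline and no known doxycycline reaction. The protocol gives no value; the range below is an assumption.

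Formulas: expected number = 65 × p; chance of at least one = 1 − (1 − p)^65.

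| Assumed p | Expected number among 65 | Chance of at least one |
|---|---|---|
| 0.1% | 65 × 0.001 = 0.065 | 1 − 0.999^65 = 6.3% |
| 0.5% | 65 × 0.005 = 0.325 | 1 − 0.995^65 = 27.8% |
| 1% | 65 × 0.01 = 0.65 | 1 − 0.99^65 = 48.0% |

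The protocol gives no cross-reaction rate, so these figures cannot be carried forward to a number of reactions.

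**The case against.** The strongest reply has four parts.

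- **Reading.** An investigator who knows that doxycycline is a tetracycline might treat a documented class hypersensitivity as sensitivity to doxycycline. That is a reasonable clinical instinct, but it needs words that the criterion does not contain, and two sites or two screeners could differ.
- **Other safeguards.** The contraindication is in the same document, and prescribing follows ordinary practice, so a careful prescriber would probably withhold the drug. This lowers the practical risk and is conceded. It does not close the gap: section 1.3 is background and not a screening step, and section 7.1 is not an eligibility criterion.
- **Magnitude.** Nothing in the protocol anchors the 0.1% to 1% range, and a figure of 48% may sound more alarming than it is. This stands. The range only illustrates how the answer depends on an unknown prevalence. It assumes the criteria are applied literally and describes enrolment, not harm. The case rests on the mismatch in the text and not on these figures.
- **Scope.** The same sentence in section 1.3 also lists pregnancy and nursing, which neither eligibility list mentions. That is true, but it is a separate point that needs its own criteria; it does not make the allergy criterion adequate.

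**Conclusion.** The concern holds. Followed exactly, sections 6.2 and 6.3 admit a patient whom section 1.3 says should not be treated. The mismatch is certain from the text alone. Its practical size is unknown and probably small, because the patient must have reacted to a different tetracycline, more than 2 months ago, and have no known reaction to doxycycline. The consequence is confined to participant safety. The change should be made, given how little it costs, but the point does not put the trial's conclusions in doubt.

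**What to change.** Bring both allergy items up to the class named in section 1.3:

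- Section 6.3: *history of allergy or hypersensitivity to doxycycline or any other tetracycline*.
- Section 6.2: *no history of allergy or hypersensitivity to doxycycline or any other tetracycline*.
- Visit 1: put the allergy question to the patient in those terms.

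Leave the contraindication in section 1.3 as it stands. Narrowing it to doxycycline would make the sections agree by weakening the safeguard.

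The cost is one line in each list and a matching change to the Visit 1 question. No new procedure is needed. The only drawback is that a few candidates may be excluded at screening.

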7. STUDY TREATMENT

7.1 Study supplies

Study treatment will be prescribed to the patient as for normal clinical practice

7.2 Study treatment formulation, packaging and storage

The most commonly used form of this medication in Italy is Bassado (Pfizer), which will be prescribed to every patient in this study. The active ingredient is doxycycline (as doxycycline hydrate). Each tablet contains 100 mg of doxycycline (equivalent to 115.4 mg of doxycycline hydrate). The other components are: starch, sodium lauryl sulfate, lactose, alginic acid, and magnesium stearate.

7.3 Treatment Dosage, administration, and compliance

Please note the following information:

The dosage will vary depending on the treatment plan prescribed for the patient. This may involve taking 50 mg (half a tablet) daily for three months, or 100 mg (one tablet) for 15 days each month for three months.

Patients will take the medication at home without medical supervision. However, they will be able to contact the medical staff involved in the study if they have any questions or suspect any adverse events.

7.4 Device Accountability of the Medical Device

Patients will bring the used blisters to V2 in order to perform drug accountability and calculate the compliance rate.

7.5 Concomitant and permitted and not permitted treatment

Clinical Trial Protocol CPDOXY1

Comparison between continuous and pulsed oral doxycycline treatment protocols for refractory meibomian gland dysfunction - 9 months follow-up prospective study

Patients will be allowed to carry on any systemic medication except:

- Multivitamins with minerals (Iron can bind to doxycycline in the gastrointestinal tract, which may prevent their absorption into the bloodstream and possibly reduce their effectiveness).
- Other oral or systemic antibiotics
- Probiotics

Patient will not be able to assume other topical medications for blepharitis or MGD treatment during the study (ex: topical antibiotics or corticosteroids) except for topical lubricating agents

